#### Criteria for Removal from Protocol:

##### Administrative

- Protocol violations, such as non-compliance with treatment, or required follow-up evaluation, as determined by the Principal Investigator (Contact SARC for non-compliance issues; study PI will review on a case-by-case basis)
- Refusal of further treatment or withdrawal of consent by the patient
- Patient is lost to follow-up

##### Medical

- Patients with radiographic or histologic evidence of disease progression who were receiving Saracatinib (see section 7.4.2)
- All patients with radiographic or histologic evidence of disease progression that is not confined to the lung(s)
- Patients with radiographic or histologic evidence of disease progression who were receiving placebo and are not amenable to surgical resection
- If the treating physician decides that it is in the best interest of the patient to be taken off the study
- Development of any concurrent medical condition that might preclude or contra-indicate the further administration of saracatinib/placebo
- Pregnancy
- Death

#### Toxicity

- Life threatening toxicity as a result of saracatinib/placebo
- Patients who have persistent toxicity despite appropriate dose modifications
- Any unacceptable toxicity in the opinion of the Principal Investigator

Patients who are taken off study will continue to be monitored for survival determination, annually by contacting the referring/treating physician, for the duration that this study is open or a maximum of 3 years follow up.

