### **3.3 Treatment Modifications**

#### **3.3.1 Dose Modification Criteria**

Dose reductions should be applied if any of the following toxicities occur

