##### Hematological

- Any CTCAEv3 grade 4 hematological toxicity of any duration (With the exception of CTCAEv3 grade 4 neutropenia  $\leq 6$  days duration. For CTCAEv3 grade 4 neutropenia  $\leq 6$  days duration, oral therapy will be held until the neutropenia recovers to CTCAEv3 grade 1 or less, at which time oral therapy will resume at the same dose)
- Febrile neutropenia (CTCAEv3 grade 3 neutropenia with temperature  $\geq 38.5^{\circ}\text{C}$  or CTCAEv3 grade 4 neutropenia with temperature  $\geq 38.0^{\circ}\text{C}$ )
- CTCAEv3 grade  $\geq 3$  neutropenia requiring hospitalization
- CTCAEv3 grade  $\geq 3$  thrombocytopenia associated with non-traumatic bleeding (with the exception of patients on therapeutic anti-coagulation)

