##### Non-Hematological

- Any CTCAEv3 grade  $\geq 3$ , non-hematological toxicity (with the exception of alopecia, nausea and vomiting)
- CTCAEv3 grade  $\geq 3$ , hypophosphatemia (see section 3.3.3 for modified dose reduction schema)
- CTCAEv3 grade  $\geq 3$  nausea or CTCAEv3 grade  $\geq 3$  vomiting, lasting  $>24$  hours despite IV fluids, anti-emetic therapy and adequate supportive care
- Chronic CTCAEv3 grade 2 nausea or vomiting

In the event of any toxicity, of any grade, that the treating physician suspects is due to disease progression, re-evaluation of tumor status is indicated, irrespective of scheduled clinic visits.

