### 3.3.2 Dose Reduction of Oral Therapy

If a patient experiences any of the toxicities defined in section 3.3.1, or another unacceptable toxicity occurs, and the investigator considers that the event is related to the study drug, oral therapy will be stopped for a maximum of 21 days, and supportive therapy will be administered as required. If the toxicity resolves or reverts to a CTCAEv3 grade 0 or grade 1 or to the baseline (pre-study) grade within 21 days of onset, oral therapy will be restarted at a lower dose as follows:

If a patient is currently taking 175 mg, the lower dose will be 125 mg.

If a patient is currently taking 125 mg, the lower dose will be 100 mg.

A maximum of two dose decreases, for any individual patient, can be made during the study period, down to the lowest dose of 100 mg of saracatinib or placebo.

If a patient experiences any of the toxicities defined in Section 3.3.1, or another unacceptable toxicity occurs, while taking 100 mg, then the patient must be withdrawn from the study. For all patients who experience any of the toxicities defined in Section 3.3.1, or another unacceptable toxicity occurs during the study, if the toxicity does not resolve to CTCAEv3 grade 0 or grade 1 or to the baseline (pre-study) grade within 21 days of onset, then the patient must be withdrawn from the study. Patients will continue to be monitored until the toxicity has resolved.

Patients will continue to be monitored for overall survival for the duration of the study. If patients have toxicity that requires their removal from the study prior to ascertainment of disease progression, then these patients will be considered treatment failures in the time to treatment failure analysis and the duration of total treatment will be included in the time to treatment failure. However, for the progression free survival analysis, withdrawals due to toxicity will be censored, as the subject has not progressed.

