### 7.2.2 Recording Procedures for All Adverse Events

All observed or volunteered adverse events, regardless of treatment group or suspected causal relationship to study drug, will be recorded as an Adverse Event in the case report forms at each study visit. Adverse events should be collected from the time the patient provides informed consent to participate in the study until 30 days after the last dose of study medication. Events involving adverse drug reactions, illnesses with onset during the study, or exacerbation of pre-existing illnesses should be recorded. Objective test findings (e.g., abnormal laboratory test results) that result in a change in study drug dosage should also be recorded.

All AEs will be recorded on the CRFs provided. A description of the event, including its date of onset and resolution, whether it constitutes a SAE or not, the date it became serious, seriousness criteria (e.g. fatal, life-threatening, hospitalization, disability, congenital anomalies), any action taken (e.g., changes to study treatment, other treatment given and follow-up tests) and outcome should be provided along with the Investigator’s assessment of causality to the study drug, study medication and study procedure.

It will be left to the treating physician’s clinical judgment whether or not an adverse event is of sufficient severity to require that the subject should be removed from treatment. A subject may also voluntarily withdraw from treatment due to what she/he perceives as an intolerable adverse event. If either of these occurs, the subject will be given appropriate care under medical supervision until the symptoms cease or until the condition becomes stable.

The severity of toxicities will be graded in accordance with the Common Terminology Criteria for Adverse Events Version 3.0 (<http://ctep.cancer.gov/forms/CTCAEv3.pdf>). A link to CTCAE v3 is also provided in the study database in the adverse event CRFs.

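### Sections 3.3.2 and 3.7.2 give opposite mandatory outcomes for a drug-related life-threatening or unacceptable toxicity that resolves within 21 days, and the withdrawal sentences of 3.3.2 drop that section's own relatedness condition

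*Combined protocol and SAP*

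**What the plan says.** Section 3.3.1 lists the toxicities that lead to dose modification and opens with "Dose reductions should be applied if any of the following toxicities occur". The hematological list begins with "Any CTCAEv3 grade 4 hematological toxicity of any duration", apart from short-lived neutropenia. The non-hematological list covers grade 3 or higher "non-hematological toxicity (with the exception of alopecia, nausea and vomiting"), and sets no upper grade.

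Section 3.3.2 applies that list. For a listed or other unacceptable toxicity, "and the investigator considers that the event is related to the study drug", therapy is held for up to 21 days. If the event returns to grade 0 or 1, or to baseline, within 21 days of onset, "oral therapy will be restarted at a lower dose as follows". Two later sentences require withdrawal from the study. One concerns an event at 100 mg. The other concerns failure to resolve within 21 days and begins "For all patients who experience any of the toxicities defined in Section 3.3.1, or another unacceptable toxicity occurs during the study". The section ends by censoring toxicity withdrawals for PFS and counting them as failures for time to treatment failure (TTF).

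The toxicity criteria for removal from protocol (numbered 3.7.2 in the table of contents) are "Life threatening toxicity as a result of saracatinib/placebo", persistent toxicity despite dose modification, and any toxicity that the Principal Investigator finds unacceptable. Patients taken off study are then contacted annually for survival.

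Two other sections touch the point. Section 7.2.2 gives the physician in charge of care a discretion, as a matter of "clinical judgment whether or not an adverse event is of sufficient severity to require that the subject should be removed from treatment". Section 7.4.1 takes a patient off study treatment, with survival follow-up only, once unblinded because of a serious adverse event.

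**The concern.** These are instructions on whether a patient is re-exposed to study drug after an event that section 7.2.1 defines by an immediate threat to life. Two sections written as directives disagree, so a site that follows one departs from the other. The trial is multi-institutional and allows part of the follow-up at local oncology offices (section 3.4, Appendix E), so uniform practice cannot be assumed.

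The disagreement also reaches the data. A restarted patient stays on the CT schedule of section 3.4. A patient removed for toxicity is censored for PFS, counted as a TTF failure and followed only for survival. In the relatedness gap, an event unrelated to study drug could end a patient's contribution to the primary endpoint.

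**Working it through.** The plan gives no figure on this point and no arithmetic applies. The check is to take defined cases through each section.

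**Case A: a related life-threatening event that resolves.** Take a patient on 175 mg or 125 mg, still blinded, with a drug-related non-hematological toxicity of grade 3 or higher (not among the exceptions) that meets the 7.2.1 definition of life-threatening and returns to grade 1 by day 21.

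1. Section 3.3.1: the event is listed, because the criterion has no upper grade.
2. Section 3.3.2: it is related, so therapy is held. It resolved in time, so therapy is restarted at the next lower dose. The wording is directive.
3. Section 3.7.2: it is life-threatening and caused by study drug, so it is a removal criterion, with no route back after recovery. Section 3.7.1 describes progression, which appears among the same criteria, as resulting in removal; the list is therefore not merely advisory.
4. Precedence: neither section mentions the other on this point. Section 7.4.1 does not apply while the patient stays blinded.

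**Case B: a related unacceptable toxicity that resolves.** Section 3.3.2 names other unacceptable toxicity beside the listed ones and sends it to hold and restart. Section 3.7.2 names unacceptable toxicity as a reason for removal. The term is the same and the outcomes are opposite.

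**Case C: an unrelated listed toxicity.** The first paragraph of 3.3.2 gives no hold and no reduction, because the relatedness condition fails. If the event has not resolved by day 21, the later sentence requires withdrawal. At 100 mg, withdrawal is required whether or not the event resolves. Neither sentence mentions relatedness.

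| Case | 3.3.2 | 3.7.2 |
|---|---|---|
| A. Related, life-threatening, resolves by day 21 | restart at lower dose | removal |
| B. Related, unacceptable, resolves by day 21 | restart at lower dose | removal |
| C. Unrelated, listed, persists past day 21 | no hold, yet withdrawal | not addressed as such |

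**Where there is no conflict.** If a related event fails to resolve in 21 days, or occurs at 100 mg, 3.3.2 also withdraws the patient and the sections agree. Persistent toxicity despite dose modification is broadly consistent between them.

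**The case against.** The strongest reply is that 3.3 is general toxicity management and 3.7.2 names specific events that override it. Section 4.4 works like this for interstitial lung disease, where discontinuation is permanent. That reading is coherent, but the text does not state it, and it does not settle Case B, where both sections use the same term. Section 3.7.2 does name the Principal Investigator as judge of what is unacceptable, but 3.3.2 does not say that this judgment displaces its restart instruction.

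Several other replies stand and limit the point:

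- A reader might count 7.2.2 as a third prescribed outcome. It is a general discretion to stop treatment, placed in a section on recording adverse events, and can sit beside specific rules.
- A reader might set 3.3.1 against 3.3.2 on relatedness. Section 3.3.1 can fairly be read as the list that 3.3.2 puts into operation. The mismatch within 3.3.2 remains. Nor can the word toxicity be taken to imply attribution: 3.3.3 applies it to hypophosphatemia, which it says may have causes other than study drug.
- A reader might count every grade 4 blood count as a conflict. Such a value need not place the patient at immediate risk of death as 7.2.1 requires. The clear overlap is non-hematological.
- Section 7.4.1 already takes some Case A patients off treatment, since its triggers include unexpected serious events for which the assignment is needed for care or for regulatory reporting.
- Slow recovery from thoracotomy is a poor example for Case C. Therapy starts only once the physician judges that it can be tolerated (3.2.3 to 3.2.5), and return to baseline grade counts as resolution.
- A reader might infer a measurable loss of power. The documents give no toxicity-withdrawal rate, and any assumed rate would count all toxicity removals rather than those in dispute. The PFS loss comes from censoring and survival-only follow-up, which would remain after the wording is reconciled and are a separate issue.

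**Conclusion.** The point holds in a narrow form. For a related toxicity, life-threatening or unacceptable, that resolves within 21 days in a patient on 175 mg or 125 mg who has not been unblinded, 3.3.2 directs restart and 3.7.2 directs removal, with no stated order between them. Within 3.3.2, the withdrawal sentences omit the relatedness condition that governs hold and reduction, so an unrelated listed event can, on a literal reading, force withdrawal and PFS censoring.

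The conclusion rests on reading the restart sentence and the removal list as directives, as they are worded. The number of patients affected cannot be estimated from the documents and is probably a small part of all toxicity withdrawals. The weight of the point lies in conflicting instructions on re-exposure after an event with immediate risk of death, and in forced withdrawal for unrelated events. It does not lie in power.

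**What to change.** Reconcile 3.3.2 and 3.7.2, and align 3.3.1, 7.2.2 and 7.4.1 with the result:

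1. State one outcome, or an explicit order of precedence, for a related life-threatening toxicity that resolves within the hold period, and likewise for an unacceptable toxicity. Say who decides that a toxicity is unacceptable.
2. Use the same relatedness condition in the hold, dose-reduction and withdrawal sentences of 3.3.2. Check 3.3.3 as well, since it borrows that pathway with a 35-day limit.
3. Say how the physician's discretion in 7.2.2 and the removal after unblinding in 7.4.1 relate to these rules.

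Which clinical rule applies is for the sponsor's clinicians. The cost is a wording amendment and notice to sites, with no change to sample size, endpoints or analysis. The amendment will not alter PFS censoring or survival-only follow-up after removal; these need separate consideration.

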### 3.2.6 Cross-over Regimen for Patients Who Recur in the Lung While On-Study

Patients who recur in the lung while on study, and who are thought to be amenable to complete surgical resection of the recurrent tumor will be unblinded. Those patients who were receiving placebo will then have the option of undergoing surgical resection; if fully resected they will be given the option to begin oral therapy with Saracatinib.

Saracatinib will be administered as a once daily, oral dose of 175 mg, for a 28-day cycle, with no breaks between cycles. The duration of treatment with saracatinib will be thirteen 28-day cycles (364 days total). Cycle 1 Day 1 must commence no later than 6 weeks after the time of the definitive metastasectomy. Patients who cannot commence oral therapy within 6 weeks will be removed from the study.

Biological studies to determine the etiology of recurrent osteosarcoma are an important component of this protocol. Prior to metastasectomy, every attempt should be made to

insure that the tumor sample is handled properly, so that all of the biological studies can be performed (see Sections 3.6.1 and Operations Manual).

Patients who recur in locations other than the lung while on-study will be taken off study and will not be unblinded.

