### **3.7 Off Study Criteria**

#### **3.7.1 Definition of Disease Progression**

Disease progression is defined as recurrence of osteosarcoma based on radiographic evidence or histologic verification of the recurrent lesion. Disease progression is one of the criteria that results in removal from the protocol.

Patients who recur in the lung while on study and who are thought to be amenable to complete surgical resection will be unblinded.  
(see Section 7.4.2).

Those who were receiving Saracatinib will be taken off study due to disease progression.

Those patients who were receiving placebo, whose recurrence is localized to the lung and who are thought to be completely resectable, will be offered the option of undergoing further surgery followed by therapy with Saracatinib (see Section 3.2.6).

The only curative therapy for patients who have progression of disease, which in this case, is recurrence of tumor, while on saracatinib or placebo, is surgical resection of all recurrent nodules. Therefore, every attempt at complete surgical resection should be attempted in any patient who progresses/recurs. Biological analysis of these tumor samples may prove very informative in determining the etiology of osteosarcoma recurrence. Therefore, at the time of surgery every attempt should be made to send the recurrent tumor sample for biological studies (see Operations Manual). Blood sample for microarray analysis should be collected at time of recurrence only if it was not obtained at baseline. Even though patients who were receiving Saracatinib will be off study due to disease progression, if the patient consents the recurrent tumor sample should still be collected for biological studies if possible.

The date that the patient is randomized will be used as the starting date for measurements of overall survival, progression free survival and time to treatment failure. For cross-over patients, the date that Saracatinib is started will be used as the starting date for measurements of overall survival, progression free survival and time to treatment failure. Progressive disease will be defined as recurrence of osteosarcoma based on radiographic evidence of recurrent nodules. In many cases, initial radiographic scans may not provide clear evidence of recurrence, especially if an infectious etiology is also possible. Once recurrence is verified, either by conclusive radiographic evidence or by histologic

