## **5.3 Statistical Considerations**

The primary goal of this study is to determine whether the addition of saracatinib to surgery will result in an improvement in progression free survival (PFS). The sample size will be based on being able to detect a 60% relative improvement (from 33% to 53%) in PFS probability at two years. The current 2-year PFS probability is 33%, when a second surgical complete remission is achieved (3). Assuming exponential survival curves, the hazard rate corresponding to this 2-year PFS probability for the control arm is 0.0462, which is defined as approximately a 0.0462 probability of failing each month when the 2-year PFS probability is 33%. If we assume that the 2-year PFS probability may be 53% for the saracatinib arm, the hazard is 0.0265, which then results in a hazard ratio of 1.75. Forty-four patients will need to be randomized in each arm of the study, for a total of 88 patients, over a 48-month accrual period. Follow-up of the last patient randomized must continue for an additional year. Since this study follows a phase II.5 design (35), this provides 80% power to detect a difference between the two resulting actuarial curves with a one-sided 0.10 alpha level log-rank test.

A secondary goal of this study is to determine whether the addition of saracatinib to surgery will result in an improvement in overall survival (OS). The sample size selected to evaluate PFS will also be adequate to detect a 56% relative improvement (from 45% to 70%) in OS probability at three years. The current 3-year OS probability is 45%, when a second surgical complete remission is achieved (3). Assuming exponential survival curves, the hazard rate corresponding to this 3-year OS probability for the control arm is 0.0222, which is defined as approximately a 0.0222 probability of failing each month when the 3-year OS probability is 45%. If we assume that the 3-year OS probability may be 70% for the saracatinib arm, the hazard is 0.0099, which then results in a hazard ratio of 2.24. Evaluation of the 88 patients who are randomized, over the same time frame, will provide 85% power to detect a difference between the two resulting actuarial curves with a one-sided 0.10 alpha level log-rank test.

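### After a resectable lung recurrence, survival is checked more often in placebo cross-over patients than in saracatinib patients, and no vital-status check is planned at the overall-survival cut-off

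*Combined protocol and SAP*

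**What the plan says.** All references are to the combined protocol and SAP.

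- **Saracatinib arm at progression.** Section 3.7.1: "Those who were receiving Saracatinib will be taken off study due to disease progression". The removal list in section 3.7.2 and the unblinding rule in section 7.4.2 agree.
- **Placebo arm, resectable lung recurrence.** Section 3.2.6 offers surgery and, after full resection, saracatinib: "The duration of treatment with saracatinib will be thirteen 28-day cycles (364 days total"). These patients are not on the removal list in section 3.7.2.
- **Placebo arm, other recurrences.** Under section 3.7.2, placebo patients with unresectable progression leave the study, as do patients in either arm with progression outside the lung.
- **Survival follow-up after leaving.** Section 3.7.2: "Patients who are taken off study will continue to be monitored for survival determination, annually by contacting the referring/treating physician", while the study is open or for at most three years.
- **On-study visits.** Section 3.4 schedules them about monthly during treatment, then every three and later every six months to month 36. No separate schedule is written for cross-over patients.
- **OS analysis.** Section 5.3 calls the sample size "adequate to detect a 56% relative improvement (from 45% to 70%) in OS probability at three years" and adds: "Evaluation of the 88 patients who are randomized, over the same time frame, will provide 85% power". The test is a one-sided 0.10 log-rank test.

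No section plans a vital-status check at the cut-off or states how survivors are censored for OS. Section 5.3 discusses cross-over only as something that may dilute the OS difference.

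**The concern.** The same clinical event leads to a different intensity of survival follow-up in the two arms. A saracatinib patient with a resectable lung recurrence moves to one physician contact a year. A placebo patient who crosses over is seen for roughly another year or more. If contacts are timed from recurrence, the last known status of an off-study patient is on average six months old at the cut-off, in the period when the risk of death is highest. Deaths between last contact and cut-off are then unknown, and how many are unknown depends on recurrence and on arm. Censoring at last contact does not cure this, because the timing of last contact is itself related to prognosis.

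OS is the first-listed secondary objective and has its own power statement. Section 1.2.9 says the results may supply parameters for a definitive trial, so a distorted OS hazard ratio would carry forward.

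**Working it through.** **1. Reproduce the stated 85%.** Inputs from section 5.3: 44 per arm, 48 months' accrual (taken as uniform), 12 months' further follow-up, and hazards of 0.0222 and 0.0099 per month ("the hazard is 0.0099, which then results in a hazard ratio of 2.24"). The chance of death by month 60 is 1 − e^(−12λ)·(1 − e^(−48λ))/(48λ).

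- Control: 1 − 0.766 × 0.615 = 0.529; × 44 = 23.3 deaths.
- Saracatinib: 1 − 0.888 × 0.796 = 0.293; × 44 = 12.9 deaths.
- Total: 36.2 deaths.

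Freedman power is Φ(√36.2 × (2.24 − 1)/(2.24 + 1) − 1.282) = Φ(1.02) = 84.6%. The Schoenfeld formula gives 87.3%. The stated 85% therefore counts every death up to month 60.

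**2. Model death after recurrence.** Recurrence follows the section 5.3 PFS hazards, 0.0462 for control and, for saracatinib, "the hazard is 0.0265, which then results in a hazard ratio of 1.75". Death follows recurrence at hazard μ, so S(t) = e^(−λt) + [λ/(μ − λ)]·(e^(−λt) − e^(−μt)). Solving at 36 months gives:

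- Control, μ = 0.0572: 0.190 + 4.21 × (0.190 − 0.128) ≈ 0.45.
- Saracatinib, μ = 0.0354: 0.385 + 2.98 × (0.385 − 0.280) ≈ 0.70.

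**3. Add the follow-up rule.** These are assumptions:

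- Off-study patients are contacted every 12 months from their own recurrence, and information stops at month 60.
- Patients without recurrence are current at the cut-off.
- A share f of placebo recurrences crosses over. The documents do not give f.
- Cross-over patients are current for about 14.5 months after recurrence. This stands for time to resection and start of drug plus 364 days of treatment.
- Cross-over has no treatment effect, which isolates follow-up. OS runs from randomisation in both arms, and the three-year limit is ignored.

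**4. Deaths known at month 60 (design alternative).** Full capture gives 22.9 placebo and 13.1 saracatinib deaths, 36.0 in all. With annual contact the saracatinib figure is about 10.3, so (13.1 − 10.3)/13.1, or about 21–22%, are missed.

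- No cross-over: 18.5 + 10.3 = 28.8 known, 7.2 missing.
- Half cross over and keep the section 3.4 visit schedule: 20.4 + 10.3 = 30.7 known, 5.3 missing.
- At 80% on that schedule: 21.4 + 10.3 = 31.7 known, 4.3 missing.

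**5. One-sided type I error with no OS effect (nominal 0.10).**

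| How OS is recorded | f = 30–80% |
|---|---|
| Everyone censored at last contact | about 0.11–0.14 |
| Patients not known dead carried as alive to cut-off | about 0.13–0.18 |
| Deaths reported as they occur, survivors censored at last annual contact | about 0.07–0.10 |

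With no cross-over the error rate stays at about 0.10. If cross-over patients are followed more closely still (the full visit schedule, or current right up to the cut-off), the first two rows reach 0.15 and 0.24 at f = 80%. Under those closer-follow-up assumptions and f = 20–80%, the null hazard ratio (saracatinib to placebo) is 0.98–0.93, 0.95–0.83 and 1.01–1.07 for the three rows.

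**6. Power.** Simulated power with full capture is about 86.5%. It is about 79–83% with annual contact and no cross-over, and about 84–89% with cross-over. The higher figures are not a gain, because the tilt in row 5 offsets the lost events.

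**7. With a common status check.** About 36 deaths, type I error about 0.10, null hazard ratio 1.00.

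**The case against.** A reader might infer that the plan under-captures deaths in the saracatinib arm and so favours saracatinib. The documents do not support that as a property of the plan, for five reasons.

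- **Direction depends on an unwritten rule.** If deaths reach the coordinating centre as they occur while survivors are censored at last annual contact, the bias runs against saracatinib. Section 7.3.1 requires deaths, as serious events, to be reported within 24 hours. That helps only partly, because section 7.2.2 ends adverse-event collection 30 days after the last dose.
- **Annual contact is not confined to saracatinib.** Placebo patients with unresectable or non-lung recurrence get it too. The tilt scales with the cross-over share, which the documents do not give, and regular visits for cross-over patients are implied rather than scheduled.
- **Contact timing is assumed.** Section 3.7.2 says only that contact is annual. A common calendar date, or a contact at study closure, is not excluded.
- **The cut-off may be later.** Section 5.3 implies month 60, but section 3.1 projects six years. With OS analysed at month 72 and censoring at last contact, about 42 deaths are known, power is about 0.90–0.91 and type I error is about 0.11 or less at 30–50% cross-over.
- **Lost power and tilt do not add.** The 79–83% figure belongs to no cross-over, where there is no tilt.

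All five stand, and they limit the claim. They do not remove it: follow-up still differs by arm after the same event, and nothing written closes the gap at the cut-off.

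**Conclusion.** The concern holds in a limited form. After a resectable lung recurrence, survival follow-up depends on the arm, and no closing status check or OS censoring rule is specified. On a month-60 cut-off with contacts timed from recurrence, about 5–7 of 36 deaths would not yet be known (nearer 4 with very high cross-over and full visits), including about 3 of 13 on saracatinib. At an assumed 30–80% cross-over, the actual one-sided error of the 0.10 OS test lies between about 0.07 and 0.18, according to how deaths are reported and survivors censored. Neither a bias in favour of saracatinib nor a material loss of power can be concluded from the documents. What can be concluded is that the OS error rate is not determined by the plan as written. OS is secondary, section 1.2.9 calls the trial's results not definitive, and primary PFS is untouched by this mechanism. It is worth correcting because the correction is cheap and works under every rule examined.

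**What to change.** In section 3.7.2, keep the annual contact and add that, before the OS analysis and any other analysis that uses OS, sites confirm vital status and the date last known alive for every randomised patient. This covers both arms, on or off study, close to one common cut-off date. It should apply regardless of the three-year limit and be subject to any withdrawal of consent to follow-up. State that deaths up to the cut-off are counted and that survivors are censored at the common cut-off or at the confirmed date.

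While editing, reconcile the OS start date for cross-over patients: section 3.7.1 restarts the clock at the start of saracatinib, whereas section 5.3 measures OS from randomisation.

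The cost is one call or e-mail per surviving off-study patient at each such analysis, plus a short protocol change. No visit, procedure or treatment rule changes.
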